## 2.0 Scientific/Safety Endpoints

*2.1 Describe the scientific endpoint(s), the main result or occurrence under study.*

*NOTE: Scientific endpoints are outcomes defined before the study begins to determine whether the objectives of the study have been met and to draw conclusions from the data. Include primary and secondary endpoints. Some example endpoints are: reduction of symptoms, improvement in quality of life, or survival. Your response should not be a date.*

The scientific endpoint of this project is determining if the study is feasible in terms of the proposed approach and if the planned outcome measures are appropriate for detecting change in the maternal dependent variables in all three participant groups.

## 3.0 Background

*3.1 Provide the scientific or scholarly background, rationale, and significance of the research based on the existing literature and how it will contribute/fill in gaps to existing knowledge.*

Physical activity during pregnancy has substantial benefits for maternal and fetal health including: reduced risk of excessive weight gain, developing pre-eclampsia (PE), gestational diabetes mellitus (GDM) and gestational hypertension (GH), pre-term birth, macrosomia; depressive symptoms, and developing childhood obesity; and, can improve maternal sleep; and neonatal neuromotor skills at 1-month of age. Despite the fact that African American women are two times more likely to have a pre-term delivery, have a higher pre-pregnancy body mass index (BMI) than Caucasian women and have a higher obesity rate, non-Caucasian pregnant women are less likely to engage in exercise and participate in more sedentary activity compared to Caucasian pregnant women. Therefore, interventions that increase exercise adherence in a prescription that is achievable and sustainable for pregnant women across a wide demographic is of critical importance for optimal maternal and neonatal outcomes.

Evidence suggests that cardiovascular exercise performed at moderate intensity starting in the first trimester and continuing until birth is not associated with an increased risk for preterm birth (<37 weeks)

or low birth weight, even in previously sedentary women; and, does not compromise maternal or fetal health as assessed by mean gestational age, type of delivery, incidence of preterm delivery, birthweight, neonatal head circumference, Apgar score or neonatal complications. A major benefit of exercise during pregnancy is assistance with weight control since excessive weight gain and inactivity are a risk factor for pregnancy complications including GDM, GH, and macrosomia. Modest increases in maternal BMI beyond standard ranges are associated with increased risk of stillbirth and neonatal, perinatal and infant death. Furthermore, pre-natal exercise has been associated with a reduction in pre- and post-natal depression with some evidence for improvement in sleep quality, fatigue, and quality of life.

Besides being associated with higher Apgar scores, exercise during pregnancy has been linked to decreased risk for childhood obesity and has been demonstrated to increase serum growth factors in neonates which may have beneficial implications for brain health and cognitive performance in the developing fetus. Infants of mothers who exercised during pregnancy demonstrated higher neuromotor abilities at 1-month of age than infants of mothers who did not exercise. Therefore, in order to minimize negative health prenatal outcomes and to maximize beneficial health outcomes in the pre and post-natal period, it is imperative that we discover how to promote participation and adherence to an appropriate pre-natal exercise intervention across a spectrum of demographics.

## 4.0 Study Design

4.1 Describe and explain the study design (e.g. case-control, cross-sectional, experimental, interventional, longitudinal, and observational). Indicate if there is randomization, blinding, control group, etc. If randomizing, explain how this will be

*achieved. For studies that have a complex study design (i.e., multiple arms and treatments), include a schematic diagram.*

This is a pilot investigation (feasibility) of a future larger study of interventional design with randomization. Participants in the pilot phase of the project will be randomized using a free online research randomizer (randomizer.org).

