### **1.0 Objectives**

*1.1 Describe the purpose, specific aims, or objectives of this research. Specifically, explain why it is important to do the study.*

Historically, pregnant women were advised to refrain from exercise due to concerns of maternal and fetal risk such as preterm delivery, low infant birth rate and fetal stress. Despite current research that has demonstrated substantial benefits for maternal, fetal, and infant health, only 9-15% of pregnant women meet the current physical activity recommendations. In addition, pregnancy exercise research is confounded by a lack of randomized controlled trials (RCT) that include diversity in participant demographics, specifically inner city populations, and difficulty accurately quantifying weekly exercise volume. We propose a pilot RCT investigating two different approaches to exercise intervention across a spectrum of demographics that we believe will result in improved exercise adherence as well as in maternal and infant health outcomes.

*1.2 State the hypothesis to be tested, if applicable.*

*NOTE: A hypothesis is a specific, testable prediction about what you expect to happen in your study that corresponds with your above listed objectives.*

Specific Aim #1: To determine the feasibility of two types of exercise interventions (supervised & home exercise) in terms of design, implementation and adherence. Our working hypothesis is that both supervised and home exercise interventions will be implementable as designed in pregnant women as evidenced by recruitment, eligibility, retention, follow-up and exercise adherence from 1st trimester through 6-months post-natal at a 60% rate, but that adherence to the two types of exercise interventions will differ by demographic. A secondary exploratory hypothesis is that we will be able to successfully recruit and retain 50% of our pregnant women from the Syracuse Community Health Center (primarily women with lower resources).

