## **5.0 Data Management and Analysis**

*5.1 Describe the data analysis plan, including any statistical procedures. This section applies to both quantitative and qualitative analysis.*

Statistical analysis used to determine feasibility of the exercise intervention will include general descriptive statistics to assess recruitment, eligibility, retention, follow-up and exercise adherence. In addition, we will conduct a survey and interview of subjects related to acceptability to participate in EX and HOMEEX and discuss barriers to regular exercise which will be analyzed using descriptive statistics and a phenomenological approach. To determine the feasibility of maternal and infant outcomes, Kruskal-Wallis and Friedman's ANOVA will be used to investigate between group and within group differences. Relationships between variables will be analyzed using Spearman correlation coefficient. Because this is a feasibility study, the results will be used as preliminary data to apply for future funding and also will provide variable quantitative and qualitative data for validating interventions that can increase adherence to exercise guidelines during pregnancy in women with different ethnic and socioeconomic backgrounds.

*5.2 If applicable, provide a power analysis for the number of subjects to be included. If qualitative research, so state, and provide general justification for the total number of subjects proposed.*

*NOTE: This may not apply to certain types of studies, including chart/records reviews, survey studies, or observational studies. This question is asked to elicit whether the investigator has an adequate sample size to achieve the study objectives and justify a conclusion.*

This is a pilot project aimed to investigate feasibility of approach and appropriateness of maternal outcome measures. If the working hypotheses are supported, the next phase will be a large, randomized intervention study. Pilot data from this project can be utilized in the power analysis for the larger study.

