## **6.0 Local Number of Subjects**

6.1 *Indicate the total number of subjects who will be enrolled or records that will be reviewed through Upstate.*

No more than 18 total participants (six per group)

6.2 *If applicable, indicate your screen failure rate, i.e., how many subjects you expect to screen to reach your target sample.*

54 (anticipate that for every three women screened, one will participate in the study)

6.3 *Justify the feasibility of recruiting the proposed number of eligible subjects within the anticipated recruitment period. For example, how many potential subjects do you have access to? What percentage of those potential subjects do you need to recruit?*

The feasibility of recruitment is part of what is being investigated in this pilot project and findings from this project will inform the recruitment plan of the future large intervention study. The plan for the pilot is to recruit no more than 18 (six per group) low risk pregnant women with a singleton pregnancy from Syracuse Community Health Center (50%), University OB/GYN Associates, and Upstate Community OB/GYN. All women will be enrolled during the 1st trimester (6 to 13-weeks' gestation) and without absolute contraindications to moderate intensity exercise during pregnancy as defined by American College of Sports Medicine (ACSM) and American College of Obstetricians and Gynecologists (ACOG). All participants will be cleared for exercise by their OB/GYN.

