## 10.0 Recruitment Methods

- N/A: Subjects will not be recruited.

10.1 Describe source of subjects: When, where, and how potential subjects will be recruited.

*NOTE: Recruitment refers to how you are identifying potential participants and introducing them to the study; for example, physician referral, database search, reviewing medical records, research participant groups/help/advocacy groups, advertising companies, call centers, in person announcements / presentations, etc.*

Participants will be recruited via physician referral, posted flyers and internet postings (e.g. local mom's groups, Upstate announcements, Department of Physical Therapy Education Facebook page, etc)

*10.2 Describe how you will protect the privacy interests of prospective subjects during the recruitment process.*

*NOTE: Privacy refers to an individual's right to control access to him or herself. This is NOT asking about confidentiality of data.*

All screening and information exchanges with prospective participants will happen in private (in a one on one setting).

*10.3 Identify all materials that will be used to recruit subjects and upload copies of these documents (such as telephone scripts, flyers, questionnaires, posters, letters, e-mails, pamphlets, advertisements).*

Flyers, e-mails

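### Does the pilot need allocation stratified by clinic to describe how adherence differs by demographic?

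*Combined protocol and SAP*

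**What the plan says.** Section 4.1 describes a feasibility pilot for a later, larger randomised study and says of allocation only: "Participants in the pilot phase of the project will be randomized using a free online research randomizer (randomizer.org". Section 9.1 adds that obstetric clearance comes before randomisation, and Section 11.0 that women are assigned at random to one of three groups. No section mentions strata, blocks or minimisation.

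Section 6.1 sets the size: "No more than 18 total participants (six per group". The Section 11.1 timetable repeats six in each arm. Sections 6.3 and 11.0 plan half of the women from SCHC, that is 9 of 18. Section 10.1 widens the sources: "Participants will be recruited via physician referral, posted flyers and internet postings".

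Aim 1 (Section 1.2) predicts feasibility in terms that include "retention, follow-up and exercise adherence from 1st trimester through 6-months post-natal at a 60% rate", and adds that "adherence to the two types of exercise interventions will differ by demographic". A secondary, exploratory hypothesis is that the team can "recruit and retain 50% of our pregnant women from the Syracuse Community Health Center (primarily women with lower resources".

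Section 5.1 assigns these quantities "general descriptive statistics to assess recruitment, eligibility, retention, follow-up and exercise adherence". It plans no test of adherence between arms or between demographic groups. It says the data should help with interventions for "women with different ethnic and socioeconomic backgrounds".

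**The concern.** Recruitment is planned by clinic, but the described allocation ignores clinic. One natural reading of Aim 1 is that adherence is to be set out by programme and by demographic. With SCHC standing in for lower resources, that is a table of four cells: EX and HOMEEX, each split into SCHC and other women. Nothing in the allocation ensures that every cell is filled, and with six women per arm chance alone can leave one nearly bare. If SCHC recruits below its target, this becomes more likely. At stake would be the descriptive by-demographic adherence result, which is part of the working hypothesis. Allocation can be set only before enrolment, so the gap could not be repaired later.

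**Working it through.** **Inputs.** N = 18 in three arms of 6 (Sections 6.1 and 11.1; 3 × 6 = 18). SCHC women S = 0.50 × 18 = 9 (Sections 6.3 and 11.0). Retention target 60% (Section 1.2). The documents give no probability of clinic balance, so there is no figure of theirs to reproduce. S = 7 and S = 6 are assumed shortfalls. Clinic means SCHC versus everyone else.

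**Chance of a small cell.** Let a, b and c be the SCHC counts in EX, HOMEEX and the control arm. With arms fixed at six,

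P(a, b, c) = C(6,a) · C(6,b) · C(6,c) / C(18,S), with a + b + c = S.

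No cell holds 0 or 1 woman when a and b both lie between 2 and 4. For S = 9:

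| (a, b) | c | ways |
|---|---|---|
| (2,2) | 5 | 15·15·6 = 1,350 |
| (2,3), (3,2) | 4 | 2·15·20·15 = 9,000 |
| (2,4), (4,2) | 3 | 2·15·15·20 = 9,000 |
| (3,3) | 3 | 20·20·20 = 8,000 |
| (3,4), (4,3) | 2 | 2·20·15·15 = 9,000 |
| (4,4) | 1 | 15·15·6 = 1,350 |

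The sum is 37,700 of C(18,9) = 48,620, so P(at least one cell of 0 or 1) = 1 − 0.7754 = 22.5%.

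The same count gives 1 − 19,200/31,824 = 39.7% for S = 7 and 1 − 7,825/18,564 = 57.8% for S = 6. If arm sizes were not fixed at six, the S = 9 figure would be 48.4%; Section 6.1 states six per group.

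**What 22.5% covers.** It is the chance for any of four cells. For one named cell at S = 9:

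[C(9,0)·C(9,6) + C(9,1)·C(9,5)] / C(18,6) = (84 + 1,134) / 18,564 = 6.6%.

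For an empty cell, each arm contributes 2 × 84/18,564. Both arms together, less the overlap of 40/48,620, give 1.7%.

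**A second reading of Aim 1.** If adherence is compared by demographic across the 12 exercising women, the control arm can take at most 6 of the 9 SCHC women. Each clinic group therefore always has at least 3 of the 12. With S = 7, a group has 2 or fewer only when the control arm draws 5 or 6 SCHC women: [C(7,5)·11 + 7] / 18,564 = 238/18,564 = 1.3%.

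**What stratifying buys.** Two lists in blocks of 3 with S = 9 give exactly 3 women per cell.

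- *Information per cell.* The most extreme contrast, 3/3 against 0/3 adherent, has a two-sided Fisher p of 2/20 = 0.10. The exact 95% interval for 3/3 starts at 0.025^(1/3) = 29%.
- *After drop-out at 60% retention (independent losses).* A cell of 3 keeps 0 or 1 woman with probability 0.4³ + 3·0.6·0.4² = 0.352. For any of four cells this is 1 − 0.648⁴ = 82%. Averaging the same calculation over the unstratified allocations gives 90%.
- *At 80% retention (assumed).* 1 − 0.896⁴ = 36%, against 62% unstratified.
- *EX–HOMEEX adherence difference.* Assume binary adherence averaging 60%, no programme effect and a 30-point clinic gap (45% and 75%). Stratified variance: 2 × (3·0.45·0.55 + 3·0.75·0.25)/36 = 0.0725, SE 26.9 points. Unstratified allocation adds (0.30/6)² · Var(a − b) = 0.0025 × 3.18 = 0.0079, SE 28.4 points. The reduction is 5% (2% to 9% for gaps of 20 to 40 points).

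**What stratifying costs.** In blocks of 3 the last allocation of each block follows from the first two, so up to 6 of 18 can be deduced by someone who knows the block size and the earlier allocations. One shuffled 6/6/6 list gives Σ 3·C(6,k)/C(18,k), k = 1 to 6, = 1.4. Under Section 14.3 the same small team supervises EX, contacts HOMEEX and does the follow-up testing. If a clinic list stops mid-block, arms can end at 5 to 7 instead of six.

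**The case for a change.** The best case for the concern is that the by-demographic hypothesis stands in Aim 1, that SCHC is the only demographic marker with a recruitment target, and that it is known before randomisation. A small trial is where chance imbalance is most likely, and a second list costs little. Blocks of 3 remove the small-cell risk at allocation altogether for 6 to 9 SCHC women, and if retention reached 80% much of that gain would survive (36% against 62%). Section 5.1 also names no table of adherence by demographic group.

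The arithmetic in that case stands. It shows that stratifying would be defensible, not that omitting it is an error. Clinic is only a proxy: Aim 1 does not define demographic, Section 5.1 speaks of ethnicity and socioeconomic position, SCHC patients are only mainly women with lower resources, and flyer or internet recruits would fall in the other stratum whatever their means. The higher figures of 40% and 58% rest on assumed shortfalls. As for the table, Aim 1 states the hypothesis and Section 5.1 already plans descriptive statistics for adherence. A breakdown by group is the obvious way to report it, and its absence from the text leads to no wrong result.

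**Conclusion.** The concern does not hold. The protocol describes no strata, and with arms of six and 9 SCHC women the chance of at least one cell with 0 or 1 woman is indeed 22.5%. This is chance variation in the size of descriptive cells. It introduces no systematic bias, does not confound SCHC with other women within an arm, leaves the overall recruitment, retention and 60% adherence rates untouched, and changes the SE of the EX–HOMEEX difference by about 5% under the assumed 30-point gap. Stratifying would give at most 3 women in the smallest proxy-defined cell, would lose most of its benefit if retention only meets the 60% target, and would make allocation easier to predict. Statisticians may reasonably differ on that trade. Leaving an 18-woman feasibility pilot unstratified is within normal practice and contradicts nothing in the documents. The conclusion rests on arms fixed at six, adherence being described and not tested, and the pilot serving to plan a larger trial, all as the plan states.

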## **5.0 Data Management and Analysis**

*5.1 Describe the data analysis plan, including any statistical procedures. This section applies to both quantitative and qualitative analysis.*

Statistical analysis used to determine feasibility of the exercise intervention will include general descriptive statistics to assess recruitment, eligibility, retention, follow-up and exercise adherence. In addition, we will conduct a survey and interview of subjects related to acceptability to participate in EX and HOMEEX and discuss barriers to regular exercise which will be analyzed using descriptive statistics and a phenomenological approach. To determine the feasibility of maternal and infant outcomes, Kruskal-Wallis and Friedman's ANOVA will be used to investigate between group and within group differences. Relationships between variables will be analyzed using Spearman correlation coefficient. Because this is a feasibility study, the results will be used as preliminary data to apply for future funding and also will provide variable quantitative and qualitative data for validating interventions that can increase adherence to exercise guidelines during pregnancy in women with different ethnic and socioeconomic backgrounds.

*5.2 If applicable, provide a power analysis for the number of subjects to be included. If qualitative research, so state, and provide general justification for the total number of subjects proposed.*

*NOTE: This may not apply to certain types of studies, including chart/records reviews, survey studies, or observational studies. This question is asked to elicit whether the investigator has an adequate sample size to achieve the study objectives and justify a conclusion.*

This is a pilot project aimed to investigate feasibility of approach and appropriateness of maternal outcome measures. If the working hypotheses are supported, the next phase will be a large, randomized intervention study. Pilot data from this project can be utilized in the power analysis for the larger study.

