Specific Aim #2: To determine the appropriateness of the outcome measures proposed for the exercise intervention in detecting changes in maternal aerobic fitness, quality of life (QOL), fatigue, sleep quality, depression, and weight change throughout pregnancy and 6-months post-natal as measured by the Balke Ware submaximal test; SF-12 Generic Quality of Life (QOL); Multidimensional Fatigue Inventory (MFI); Pittsburgh Sleep Quality Index (PSQLI); Center for Epidemiologic Studies Depression Scale (CES-D); Edinburgh Postnatal Depression Scale (EPDS); and the Pregnancy Physical Activity Questionnaire (PPAQ). Our working hypothesis is that the above outcome measures will be able to detect changes in maternal outcome measures in both exercise groups.

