submaximal treadmill test to determine HRR for the two exercise groups and estimate VO2max using the Pollock equation which will be repeated at 3- and 6-months after birth to compare aerobic fitness levels.

All women will complete the following questionnaires at baseline (late 1st trimester), 25-26 weeks (late 2nd trimester), and 37-38 weeks (late 3rd trimester), and monthly through 6-months post-natal: MFI, SF-12 QOL; PSQLI; CES-D; EPDS; and the PPAQ. All questionnaires have been demonstrated to have good validity, reliability, and internal consistency and the CES-D and EPDS are similar to each other in regards to internal consistency and test-retest reliability.

Infants from mothers in all three groups will have their gross and fine motor, and cognitive development measured monthly (months 1-6) at home using the Bayley Scales of Motor Development, 4th edition. The Bayley 4 is a standardized, norm-referenced tool with subtest level scaled scores, domain level composite scores, percentile ranks, and developmental age equivalents. Infant height and weight will be measured monthly through 6-months of age.

Women assigned to EX will have all of their supervised pregnancy exercise sessions, questionnaires, and weight measured at the IHP. After delivery, women assigned to EX will resume their supervised IHP exercise program between 4-8 weeks (depending on delivery mode) when they are cleared for activity by their physician, complete exercise testing at 3- and 6-months and will have monthly home visits for infant testing through 6 months. HOMEEX and UC women will visit the IHP at baseline, 3 & 6-months post-delivery for exercise testing, questionnaires, and weight measurement. HOMEX and UC groups will receive home visits for: 2nd & 3rd trimester questionnaires and weight measurement and every month post-delivery for questionnaires, weight measurement and infant testing.

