Statistical analysis used to determine feasibility of the exercise intervention will include general descriptive statistics to assess recruitment, eligibility, retention, follow-up and exercise adherence. In addition, we will conduct a survey and interview of subjects related to acceptability to participate in EX and HOMEEX and discuss barriers to regular exercise which will be analyzed using descriptive statistics and a phenomenological approach. To determine the feasibility of maternal and infant outcomes, Kruskal-Wallis and Friedman's ANOVA will be used to investigate between group and within group differences. Relationships between variables will be analyzed using Spearman correlation coefficient. Because this is a feasibility study, the results will be used as preliminary data to apply for future funding and also will provide variable quantitative and qualitative data for validating interventions that can increase adherence to exercise guidelines during pregnancy in women with different ethnic and socioeconomic backgrounds.

In order to monitor the safety of the participants, all exercise performed by the EX, HOMEEX, and UC groups will follow ACSM and ACOG guidelines for moderate-intensity cardiovascular and resistance exercise. In addition, all women will wear a Polar Ignite watch that will alarm if their HR exceeds moderate level intensity. All women in the EX will be supervised during their exercise sessions. Women in the HOMEEX group will be meet individually with either [name] or [name] to discuss safe exercise principles. They will be given written information on exercising in a moderate intensity range for both cardiovascular and resistance exercise. In addition, they will be contacted twice per week to discuss their program and any questions about exercise. Lastly, their HR data will be downloaded and analyzed to confirm that they are exercising in a moderate intensity rate. Women in the UC group will be told to continue participating in whatever activity they are currently engaged. They will be given an activity log to record their activity and we will download their HR data.

*11.1 Describe what data, including long-term follow-up, will be collected.*

*NOTE: For studies with multiple data collection points or long-term follow up, consider including a schedule or table in your response.*

Instruments being utilized in this study:

- The Bayley Scales of Infant Development, 4th edition
- Physical Activity diary

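### Outcome feasibility is to be determined by Kruskal-Wallis and Friedman tests, which do not measure whether the assessments can be collected; completion per instrument and visit should be reported instead

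*Combined protocol and SAP*

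**What the plan says.** Section 5.1 separates two feasibility questions and gives each a method; section 11.0 repeats the text.

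- **Exercise intervention:** "general descriptive statistics to assess recruitment, eligibility, retention, follow-up and exercise adherence". Aim 1 in section 1.2 supplies the target: "recruitment, eligibility, retention, follow-up and exercise adherence from 1st trimester through 6-months post-natal at a 60% rate". A survey and interview cover the acceptability of taking part in EX and HOMEEX and barriers to exercise.
- **Outcomes:** "To determine the feasibility of maternal and infant outcomes, Kruskal-Wallis and Friedman's ANOVA will be used to investigate between group and within group differences".

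For the maternal measures, Aim 2 asks about change: "Our working hypothesis is that the above outcome measures will be able to detect changes in maternal outcome measures in both exercise groups". The section 2.1 endpoint is similar; it asks "if the planned outcome measures are appropriate for detecting change in the maternal dependent variables in all three participant groups". Section 5.2 makes the larger trial depend on the working hypotheses being supported.

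Infant outcomes are in neither aim nor the endpoint, although section 11.0 schedules them in full: "Infants from mothers in all three groups will have their gross and fine motor, and cognitive development measured monthly (months 1-6) at home". Section 19.4 limits the neonatal portion to infants born at 37 weeks or later.

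**The concern.** Whether an outcome is feasible to collect depends on how many of the planned assessments were obtained and usable. A difference test answers another question. An instrument completed by every woman may show no difference between arms or visits, and one with many missing forms may show a difference by chance or because the effect is large.

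Feasibility is part of the stated scientific endpoint, and the pilot is meant to inform a larger trial. The measurement schedule is heavy. It is also delivered differently by arm: EX women complete their prenatal questionnaires at the IHP, while HOMEEX and control women are visited at home for the second- and third-trimester ones. Whether this schedule can be completed, and equally in each arm, is something the next trial needs to know. The named method does not provide it, and for infants no other criterion is given.

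**Working it through.** **Inputs from the documents.** At most 18 women, six per group (6.1). Six questionnaires at three prenatal points and monthly for six months after birth; a treadmill test at baseline, 3 and 6 months; six monthly infant assessments (11.0). Full-term infants only (19.4). The plan's figures reproduce: 3 × 6 = 18 enrolled, and 18 × 3 = 54 screened. Neither is disputed. No alpha, SD, effect size or power is stated, so there is no power calculation to reproduce.

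**Step 1: assessments due (maxima).**
- Questionnaires: (3 + 6) occasions × 6 instruments = 54 per woman; 54 × 18 = 972.
- Treadmill tests: 3 × 18 = 54.
- Infant assessments: 6 × 18 = 108, fewer if any infant is born before 37 weeks.

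**Step 2: what Kruskal-Wallis responds to.** H = [12 / (N(N+1))] Σ(Rⱼ² / nⱼ) − 3(N+1), referred to chi-square on 2 df. N and nⱼ count the values observed, and Rⱼ is the rank sum in arm j. The number of assessments due does not enter.

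Simulated share of pilots with p < 0.05 (6,000 runs per cell). Assumptions: alpha 0.05, normal data, one value per participant, equal shift in both exercise arms.

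| Collected | 0 SD | 0.5 SD | 1 SD | 2 SD |
|---|---|---|---|---|
| 6 per arm (18/18, 100%) | 3.7% | 10.1% | 30.5% | 87.0% |
| 4 per arm (12/18, 67%) | 4.0% | 7.4% | 17.7% | 59.6% |

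A separate run of 2,500 per cell agreed within one percentage point. With no arm effect the rate is about 4% whether all or two-thirds of the values were collected, so the test cannot tell these situations apart. At a fixed non-zero effect, missing data do lower the rate, but only by reducing n.

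**Step 3: Friedman.** Within one arm of 6 (assumed: within-woman correlation 0.5, linear drift, alpha 0.05; 1,500 runs), significance is reached in 14% to 36% of pilots over 3 time points, and 10% to 44% over 9, for total changes of 0.5 to 1 SD. The test also needs complete rows. If each visit is completed independently with probability p, the share of women with all nine occasions is p⁹:
- p = 0.95: 0.95⁹ = 0.630, and 18 × 0.630 = 11.3 women.
- p = 0.90: 0.90⁹ = 0.387, and 18 × 0.387 = 7.0 women.

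Missed visits would shrink the analysed set without appearing as a feasibility result.

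**Step 4: what a completion proportion gives.** Exact (Clopper-Pearson) 95% limits solve P(X ≥ x | p) = 0.025 for the lower and P(X ≤ x | p) = 0.025 for the upper. At x = n the upper limit is 1.
- 18/18: 82% to 100%.
- 15/18: 59% to 96%.
- 11/18: 36% to 83%.
- 4/6 (one arm): 22% to 96%.

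If the 60% rate were applied to an instrument, at least 11 of 18 would be needed (11/18 = 61%; 10/18 = 56%). The binomial chance of reaching 11 is 5.8% if true completion is 40%, 56% if it is 60%, and 98% if it is 80%. These intervals are wide, but they concern the right quantity.

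**The case against.** The strongest reply is that the sentence uses feasibility loosely and really serves Aim 2. That aim, the section 2.1 endpoint and section 5.2 ask whether the maternal measures are appropriate, which the first two tie to detecting change. Within-group testing is a reasonable way to look at that, and this part of the reply stands. It does not extend to the infant outcomes, which the sentence includes and Aim 2 does not. Nor does it make a difference test a measure of whether data can be collected.

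A second reply is that completion is already covered, because retention and follow-up are summarised against 60% and follow-up visits are where the measures are taken. This also stands in part. A reader might infer that the whole feasibility verdict ignores completion; the documents do not support that. What is missing is narrower: a woman can be retained and visited while a form, treadmill test or infant assessment is missed, and no count by instrument and visit is planned.

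A third reply is that nothing says a significant test means feasible or a non-significant one means not feasible. That is correct. A reader might turn the rates in the table into the share of pilots in which a fully collected outcome would be declared infeasible. The plan contains no such rule and no alpha, so the rates cannot carry that meaning. Nor does progression turn on the infant results, since neither working hypothesis covers them.

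**Conclusion.** The point holds in a limited form. Sections 5.1 and 11.0 assign difference tests to determine the feasibility of the outcomes. Those tests do not measure collectability, and no other section plans completion per instrument and visit. For infants the sentence is the only criterion.

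The size is shown by how little the tests convey at this sample size. With complete data from 6 per arm, Kruskal-Wallis is significant in about 4%, 10% and 30% of pilots at 0, 0.5 and 1 SD, so non-significance is the usual result and says little about feasibility. This rests on an assumed alpha of 0.05, normal data and an equal shift in both exercise arms. The conclusion that the tests measure something else does not depend on those assumptions.

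The documents do not support the stronger inference that the study's feasibility verdict is decided by effect size: participant-level follow-up has its own target, and no decision rule is attached to a p-value.

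**What to change.** Replace the sentence in sections 5.1 and 11.0 with wording such as:

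> The feasibility of each maternal and infant outcome will be determined by the number of usable assessments divided by the number due at each planned visit, overall and by arm, with exact 95% confidence intervals. The maternal denominator is all randomised women. The infant denominator is infants eligible for the neonatal portion (born at 37 weeks or later); the share of infants who are eligible will be reported separately. Kruskal-Wallis and Friedman results are exploratory information on change for Aim 2 and do not determine feasibility.

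Using all live-born infants as the denominator would count the exclusions planned in section 19.4 as failures.

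State the completion threshold before data are examined. The 60% rate of Aim 1 is one option; applying it to single instruments would be a new choice, because the plan sets it for recruitment, eligibility, retention, follow-up and adherence. Whether to add infant assessments to the section 2.1 endpoint is for the sponsor to decide; this fix does not require it.

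The cost is a wording change in two places and one extra table from data already collected, with no added visits, staff or participants. The p-values lose their role in the feasibility statement.
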